Treating Stimulant Addiction With Repetitive Transcranial Magnetic Stimulation (rTMS)

NCT04228276

Principal Investigator: [name]

Palo Alto VA

[contact] | [contact]

April 27, 2025

Hypothesis Testing

Primary Outcome Hypothesis: Compared to sham treated subjects, active rTMS treated subjects will show lower relapse rates. Treatment groups will be compared on their rates of relapse using Chi-square tests.

We will conduct an intent to treat (ITT) analysis for hypothesis testing. We will supplement this analysis with a per protocol analysis in which only subjects who completed all rTMS treatments will be compared. We will include an examination of whether bias has been introduced due to dropout by determining if there is greater dropout in the treatment group, and if significant differences exist in major demographic and clinical variables of individuals who have dropped out compared to those who have not. We will correct for any significant differences using covariates in our statistical models.

Our study design includes randomization to minimize selection bias. However, to address the possibility of residual confounding, we will conduct the following post-randomization analysis. We will compare the baseline characteristics of the treatment groups to identify any imbalance in demographic or other characteristics that could be confounding group comparisons. These include age, level of use of stimulants, gender, presence of and/or severity of psychiatric co-morbidity, and level of functional impairment. If imbalances are detected, we will use regression models adjusting for these variables to isolate the effect of the treatment.

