Functional status. To quantify the functional impact of SUD and changes resulting from treatment, we will utilize the Addiction Severity Index (ASI). It is an instrument specifically developed to assesses the impact of substance use disorders on several domains of function, including medical, employment/support status, legal, family/social, and psychological. It is one of the best validated and commonly used scale for research into the problems associated with substance abuse (Amin-Esmaeili et al., 2024; McLellan et al., 2010; Miguel et al., 2021). Consequently, the ASI will facilitate the integration and comparison of results from this proposal to findings in the literature. To supplement this measure, we will also apply the Community Integration Questionnaire (CIQ) (Dijkers, 1997) as an additional measure of functional change. The CIQ will complement the ASI since it is broader and more general assessment of everyday functioning in the community. Both assessments will be administered two times: pre-treatment and 3 months after completion of the last treatment session.

Randomization of subject treatment assignments, drop-outs and subject flow. We will use a modification of the Efron procedure (Efron, 1971) developed by [name] (H. Kraemer, C., 1981) to randomize

participants and to assure comparable stimulant use severity between groups at baseline. Subjects screened out during baseline (prior to randomization) will be replaced. After randomization, dropouts will not be replaced but will be retained in the statistical modeling, i.e. their data will be retained in these analyses because they are equivalent to intention to treat analyses. This minimizes loss of power and bias caused by dropouts.

Treatment Phase

rTMS stimulation parameters

2.a.3.d. Post-Treatment Phase

2.a.3.d.1. Assessment of relapse

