The primary outcome measure will be rate of relapse within a three-month period following rTMS treatment completion. Relapse within the 3-month period following treatment will be determined using the Timeline Followback (TLFB) method. Subjects will be contacted monthly to review the prior months use history if any. We will supplement this assessment with a review of electronic medical records to look for evidence of relapse, such as progress notes from clinical staff and urine toxicology results. Relapse is defined as any use of a stimulant. Frequent testing occurs for veterans enrolled in ATS at the Palo Alto VA Medical Center, where most subjects will be recruited and will continue to be seen in their treatment programs.

Secondary outcome measures will be: 1) duration of sobriety following end of treatment phase; 2) change in level of craving (assessed by 10-point Likert scale) at end of treatment phase and three month follow up compared to baseline; 3) amount of stimulant use quantified as number of days of use of stimulants normalized by baseline values.

References

Ashok, A. H., Mizuno, Y., Volkow, N. D., & Howes, O. D. (2017). Association of Stimulant Use With Dopaminergic Alterations in Users of Cocaine, Amphetamine, or Methamphetamine: A Systematic Review and Meta-analysis. *JAMA Psychiatry*, *74*(5), 511-519.

Bohnert, K. M., Ilgen, M. A., Louzon, S., McCarthy, J. F., & Katz, I. R. (2017). Substance use disorders and the risk of suicide mortality among men and women in the US Veterans Health Administration. *Addiction*, *112*(7), 1193-1201.

Camprodon, J. A., Martinez-Raga, J., Alonso-Alonso, M., Shih, M. C., & Pascual-Leone, A. (2007). One session of high frequency repetitive transcranial magnetic stimulation (rTMS) to the right prefrontal cortex transiently reduces cocaine craving. *Drug Alcohol Depend*, *86*(1), 91-94.

Cho, S. S., & Strafella, A. P. (2009). rTMS of the left dorsolateral prefrontal cortex modulates dopamine release in the ipsilateral anterior cingulate cortex and orbitofrontal cortex. *PLoS One*, *4*(8), e6725.

Cox, K. B., Malte, C. A., & Saxon, A. J. (2017). Characteristics and Service Utilization of Homeless Veterans Entering VA Substance Use Treatment Psychological Services *Psychological Services*, *14*(2), 208-213.

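### Randomisation balances baseline stimulant-use severity but the primary chi-square leaves it out; a test prespecified to adjust for severity would recover some power at almost no cost

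*SAP*

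**What the plan says.** **Allocation.** The protocol section on randomization, drop-outs and subject flow uses a modified Efron procedure to randomise "participants and to assure comparable stimulant use severity between groups at baseline". It does not give the coin probability, or say whether severity is handled as strata or on a continuous scale.

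**Primary test.** Under Hypothesis Testing, the SAP states: "Treatment groups will be compared on their rates of relapse using Chi-square tests". The analysis is by intention to treat. No covariate is named.

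**Routes by which severity could enter.**
- *Dropout.* The SAP will examine "if significant differences exist in major demographic and clinical variables of individuals who have dropped out compared to those who have not" and adds: "We will correct for any significant differences using covariates in our statistical models". No test, level or variable list is given.
- *Baseline imbalance.* Introduced with the words "to address the possibility of residual confounding, we will conduct the following post-randomization analysis", this step compares the arms on listed characteristics ("These include age, level of use of stimulants, gender", psychiatric co-morbidity and functional impairment). The SAP then says: "If imbalances are detected, we will use regression models adjusting for these variables to isolate the effect of the treatment". No criterion for imbalance is given, and the list is open-ended.

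The per-protocol analysis is expressly described as a supplement. The triggered regressions carry no such label.

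**Measurement.** In the protocol's section on severity of stimulant use, days of use over a 60-day window are recorded with the Timeline Followback (TLFB). The only analysis planned for them there is exploratory moderator work.

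**The concern.** When allocation forces the arms to be alike on a baseline factor, the treatment difference varies less from trial to trial than it would under simple randomisation. A test that ignores the factor uses the larger, unadjusted variance. If the factor predicts the outcome, the test rejects less often than its nominal level under the null, and it loses power under the alternative.

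The conditional adjustment does not reliably repair this. It looks for imbalance, and imbalance in severity is what the randomisation is built to prevent. A strong predictor of relapse could therefore be well balanced, never flagged, and left out of the primary test.

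What is at stake is efficiency, not validity. There is also a smaller matter: if a trigger does fire, the SAP does not say outright which p-value is the primary one.

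**Working it through.** **Inputs.** The plan has no power figure to reproduce. It states no sample size, alpha, relapse rate, coin probability or strength of association between severity and relapse. Everything below is assumed: two-sided 5%, severity standard normal, Efron coin 2/3 within a median split, control relapse about 50%, treatment odds ratio 0.35, all outcomes observed, severity odds ratio (OR) 1.5, 2 or 3 per SD. There were 20,000 replicates per cell (Monte Carlo error 0.15 points at 5%).

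**Step 1: why the chi-square becomes conservative.** Take two equal severity halves, perfectly balanced, with overall relapse 50%. With odds ratio R between halves, the relapse probabilities are p = √R/(1+√R) and 1−p. The chi-square uses variance 0.25; the variance that applies is p(1−p). True size = 2·[1 − Φ(1.96/√(p(1−p)/0.25))].
- R = 4: p = 0.667, variance 0.222, ratio 0.889, size 2·[1 − Φ(2.079)] = 3.8%.
- R = 10: p = 0.760, variance 0.183, ratio 0.730, size 2·[1 − Φ(2.294)] = 2.2%.

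A separate simulation with binary severity (overall relapse 60% under the null, 3,000 replicates, N = 60, 100, 200) gave 3.6–4.5% and 2.3–2.9%, in line with this.

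**Step 2: simulated chi-square size, continuous severity.**

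| Severity OR per SD | N=60 | N=100 | N=150 |
|---|---|---|---|
| 1.5 | 5.1% | 5.5% | 4.8% |
| 2 | 4.7% | 4.8% | 4.5% |
| 3 | 3.8% | 4.3% | 3.6% |

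The logistic likelihood-ratio test has size 5.2–5.7%.

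**Step 3: power at N=100.**

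| OR per SD | Chi-square | Cochran–Mantel–Haenszel (CMH) | Logistic | Logistic − chi-square |
|---|---|---|---|---|
| 1.5 | 68.8% | 68.9% | 70.0% | 1.2 |
| 2 | 64.0% | 65.4% | 67.7% | 3.7 |
| 3 | 55.8% | 59.9% | 64.2% | 8.4 |

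At OR 1.25 the figures are 70.9%, 70.5% and 71.2%, so nothing measurable is lost. Where the plan's rule rarely selects severity, its loss against logistic regression is 2.7, 4.7 and 8.8 points at N=60 for OR 1.5, 2 and 3, and 1.1, 2.9 and 7.5 at N=150.

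**Step 4: does the plan's own rule recover this?** Severity is flagged in 0.2–0.4% of trials at p<0.05, but in 33–57% if imbalance means a standardised difference above 0.1. The SAP does not say which applies. The dropout trigger was modelled with 19% dropout and a severity OR of 1.5 on dropout. Remaining loss against logistic regression at N=100 (logistic power minus the rule's power):

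| Rule | OR 1.5 | OR 2 | OR 3 |
|---|---|---|---|
| p<0.05, dropout trigger not operating | 70.0−68.8 = 1.2 | 67.7−64.0 = 3.7 | 64.2−55.8 = 8.4 |
| p<0.05 plus dropout trigger | 70.0−69.2 = 0.8 | 67.7−65.1 = 2.6 | 64.2−59.0 = 5.2 |
| Standardised difference >0.1 plus dropout trigger | 70.0−69.5 = 0.5 | 67.7−66.3 = 1.4 | 64.2−61.2 = 3.0 |

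**Step 5: cross-check.** The binary-severity simulation, with 60% versus 40% relapse, lost about 0–1 points at OR up to 2 between halves, 2–5 at OR 4 and 6–12 at OR 10. The halves of a normal score differ by 2√(2/π) ≈ 1.6 SD. OR 2 per SD is therefore about 2^1.6 = 3.0 between halves, and OR 3 per SD about 3^1.6 = 5.8. The two sets are compatible.

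**Step 6: the open choice.** Reporting the smaller of the chi-square and severity-adjusted p-values gives type I error of about 5.3–6.2% across the simulations. In one direct comparison it was 5.6–6.1%, against 5.1–5.6% for the adjusted test alone, so choosing adds about 0.4–0.7 points. Followed mechanically on severity alone, the rule gives 4.1–5.5%.

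**The case against.** The strongest reply is that leaving a balanced covariate out of a valid test is an efficiency choice and not an error. That stands. The larger losses need strong prognosis, which nothing in the documents establishes. The protocol's diagnostic assessment confirms severe disorder, which may narrow the spread of severity and push the loss towards zero. That also stands, and is why the result is given as a range.

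Several stronger readings are tempting, and the documents do not support them.
- *The triggered regression becomes the primary result.* The chi-square is the only test named under the primary hypothesis, and regression comes later as a post-randomisation step, so a supportive role is the natural reading. The SAP simply does not say so, and its dropout sentence, in the same paragraph as the ITT analysis, is less clear.
- *The plan materially inflates false positives.* The excess is small. Choosing among models under several definitions of imbalance gave 5.0–7.5%, but a single prespecified five-covariate logistic test with no choosing already has size 6.5–6.7% at N=60 and 5.4–5.7% at N=150. Much of the apparent inflation may be small-sample behaviour of logistic regression.
- *The triggers ignore prognosis.* The imbalance screen is aimed at characteristics that could confound the comparison, so relation to outcome is part of the idea. What is missing is a criterion.
- *The protocol itself treats severity as prognostic.* A secondary outcome is "number of days of use of stimulants normalized by baseline values", but that defines an outcome scale and says nothing about how well severity predicts binary relapse.

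**Conclusion.** The point holds as one of efficiency. Allocation is balanced on severity, the primary test omits it, and the conditional route is unlikely to restore it if imbalance is judged by significance. Against a prespecified severity-adjusted logistic test, the chi-square gives up about 1–3 points of power at OR 1.5 per SD, 3–5 at OR 2 and 8 at OR 3. Some of this is recovered if the triggers fire, and almost nothing is lost if prognosis is weak. All these figures depend on the assumed sample size, relapse rates, coin and association.

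A reader might infer that the trial's primary result would be invalid, or that the trial is underpowered. Neither follows: the chi-square controls type I error, and no power target is given to fall short of. The unranked adjusted result and the undefined triggers are a secondary reason to amend. The change is worth making because the covariate is already collected and already used for allocation.

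**What to change.** Name one primary ITT test that adjusts for baseline stimulant-use severity whatever imbalance is observed. An example is logistic regression of relapse on arm and severity, tested by likelihood ratio. State the variable exactly: the baseline TLFB days of use, or the severity measure that the randomisation uses, on the same scale. A CMH test is an alternative only if the algorithm uses severity strata, which the protocol does not describe. On a median split it also gave no reliable gain over the plan's own rule at OR 1.5 or 2 (−0.9 to 1.4 points).

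Add one sentence making the unadjusted chi-square, and any imbalance-triggered or dropout-triggered model, sensitivity analyses. If the sponsor prefers to keep the chi-square as primary, that is valid, but the SAP should still label the adjusted models as supportive and define the triggers.

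**Cost.** SAP wording, plus copying the severity definition from the randomisation algorithm; no new data. There are two small downsides. Logistic regression reports a conditional odds ratio, so a risk difference should be given alongside. The likelihood-ratio test can also be slightly liberal at about N=60 (5.1–6.3% in the binary-severity simulation). The documents do not state the trial's status, so the change should be made before any unblinded look at outcomes.
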